**Arm A: Avelumab + SOC CRT**  
**Arm B: Placebo + SOC CRT**
- In both treatment arms, study treatment will be initiated with a Lead-in avelumab/placebo Phase followed by a Chemoradiotherapy (CRT) Phase and a Maintenance Phase. In both arms, BSA must be calculated prior to each cisplatin administration and patient must be weighed prior to each avelumab/placebo administration. Specific therapies to be administered include the following:
- Lead-in Phase: avelumab 10 mg/kg (Arm A) or placebo (Arm B) administered on Day 1 (7 days prior to the start of the CRT phase).
  - CRT Phase: avelumab 10 mg/kg (Arm A) or placebo (Arm B) administered on Days 8, 25, and 39 in combination with cisplatin 100 mg/m^2 on Days 1, 22, and 43 plus intensity modulated-radiation therapy (IMRT) 70 Gy/35 fractions/7 weeks; 1 fraction/day, 5 fractions/week. **Cisplatin should be administered on a Monday or Tuesday if feasible to maximize overlap with IMRT.** The Day 43 dose of cisplatin can be given any time up to 5 days after the end of radiation therapy.
  - Maintenance Phase: avelumab 10 mg/kg (Arm A) or placebo (Arm B) administered Q2W for 12 months. The Maintenance Phase starts following completion of CRT Phase (ie, 2 weeks following completion of CRT).
- Patient weight should be verified prior to dose calculation for each of the study treatments.  
See Section 5.5.1.5 and 5.5.2.1 for mandatory premedications to be administered with avelumab/placebo and cisplatin, respectively.
19. **Avelumab Pharmacokinetics:** Blood samples (3.5 mL) for avelumab PK will be collected in all patients: pre-dose (within 2 hours before the start of avelumab/placebo infusion) and at the end of infusion (immediately before until 10 minutes after the end of avelumab/placebo infusion) on Days 1 of the Lead-in Phase and Days 8, and 25 of the CRT Phase.
20. **Cisplatin Pharmacokinetics:** Blood Samples (5 ml) for cisplatin PK (total and free) will be collected in a total of 24 patients (12 patients in Arm A and 12 patients in Arm B) at selected sites at pre-dose, mid-infusion, end of infusion (immediately before the end of cisplatin infusion), and 3, 4, and 24 hours post start of cisplatin infusion on Day 1 of the CRT Phase.

- |     |   |
|-----|---|
| 21. | CCI [REDACTED] CCI [REDACTED]   |

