### 1.2.2.2. Pharmacokinetics of Avelumab in Humans

Avelumab pharmacokinetics and dose proportionality following the first 1-hour infusion have been characterized in 77 Caucasian patients treated in the dose escalation and expansion cohorts of Trial EMR100070-001 by standard non-compartmental analysis. This analysis revealed that the exposure parameters of maximum concentration ( $C_{max}$ ) and area under the concentration-time curve to the end of the dosing period ( $AUC_{\tau}$ ) increased in a dose proportionate fashion for the 10 and 20 mg/kg doses. The half-life of avelumab tended to increase with dose, likely due to target mediated disposition at lower doses (1 and 3 mg/kg), but terminal half-life of 10 mg/kg ( $102 \pm 28$  hours) and 20 mg/kg ( $120 \pm 42$  hours) doses were similar, taking into account the PK variability. This likely indicates target mediated elimination does not increase at these two doses and target occupancy is very high.

Target occupancy on peripheral blood CD3+ T-cells was investigated in human blood in vitro by flow cytometry after spiking of whole blood samples from 8 healthy volunteers with avelumab over a concentration range of 0.003-10  $\mu\text{g/mL}$ . Fifty percent (50%) receptor occupancy was observed at a drug concentration of  $0.122 \mu\text{g/mL} \pm 0.042 \mu\text{g/mL}$  with a plateau indicating at least 95% receptor occupancy reached in all blood samples at 1  $\mu\text{g/mL}$ .

Pharmacokinetic profiles obtained during the dose escalation phase of Trial EMR100070-001 were utilized to investigate whether this concentration of at least 1  $\mu\text{g/mL}$  was achieved throughout the dosing interval. The median  $\pm$  standard deviation trough concentration ( $C_{trough}$ ) at the end of the first cycle after administration of the 10 mg/kg dose is  $21 \pm 12 \mu\text{g/mL}$  (n=283). This median  $C_{trough}$  increases during the subsequent cycles to  $25 \pm 16 \mu\text{g/mL}$  (second cycle) (n=269),  $27 \pm 17 \mu\text{g/mL}$  (third cycle) (n=202), and remains between 27 and 36  $\mu\text{g/mL}$  during the subsequent cycles (n=55–171).

Complete information for avelumab may be found in the single reference safety document (SRSD), which for this study is the avelumab Investigator's Brochure (IB).

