#### 4.2. Exclusion Criteria

Patients with any of the following characteristics/conditions will not be included in the study:

1. Prior immunotherapy with an anti-PD-1, anti-PD-L1, anti-PD-L2, anti-CD137, or anti-CTLA-4 antibody (including ipilimumab), or any other antibody or drug specifically targeting T cell co-stimulation or immune checkpoint pathways.
2. Major surgery  $\leq 4$  weeks prior to randomization.
3. Prior malignancy (other than the current Head and Neck cancer or in situ disease) requiring tumor-directed therapy within the last 2 years prior to enrollment, or concurrent malignancy associated with clinical instability. Exceptions for disease within the 2 years are superficial esophageal cancer (TIS or T1a) fully resected by endoscopy, prostate cancer (Gleason score  $\leq 6$ ) either curatively treated or deemed to not require treatment, ductal in situ carcinoma of the breast that has completed curative treatment, adequately treated basal cell or squamous cell skin cancer.
4. Active autoimmune disease that might deteriorate when receiving an immunostimulatory agent. Patients with diabetes type I, vitiligo, psoriasis, or hypo- or hyperthyroid disease not requiring immunosuppressive treatment are eligible.
5. Any of the following in the 6 months prior to randomization: myocardial infarction, severe/unstable angina, coronary/peripheral artery bypass graft, symptomatic congestive heart failure, cerebrovascular accident, transient ischemic attack, or symptomatic pulmonary embolism.
6. Active infection requiring systemic therapy.
7. Known prior severe hypersensitivity to investigational products or any component in the formulations, including known severe hypersensitivity reactions to mAbs, cisplatin, or platinum-related compounds (NCI CTCAE v4.03 Grade  $\geq 3$ ).
8. Use of immunosuppressive medication at time of randomization, except the following:
  - a. Intranasal, inhaled, topical steroids, or local steroid injections (eg, intra-articular injection);
  - b. Systemic corticosteroids at physiologic doses  $\leq 10$  mg/day of prednisone or equivalent;
  - c. Steroids as premedication for hypersensitivity reactions (eg, CT scan premedication).
9. Prior organ transplantation including allogenic stem-cell transplantation.

10. Diagnosis of prior immunodeficiency or known human immunodeficiency virus (HIV) or acquired immunodeficiency syndrome (AIDS) related illness.

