**Table 3. PK Parameters to be Determined for Avelumab and Cisplatin**

Parameter	Definition	Method of Determination
$AUC_{inf}$	Area under the plasma concentration-time profile from time zero extrapolated to infinite time	$AUC_{last} + (C_{last}/k_{el})$ where $C_{last}$ is the predicted plasma concentration at the last quantifiable time point estimated from the log-linear regression analysis, and $k_{el}$ is the terminal phase rate constant calculated by linear regression of the log-linear concentration-time curve. Only those data points judged to describe the terminal log-linear decline will be used in the regression.
$C_{max}$	Maximum observed plasma concentration	Observed directly from data
$T_{max}$	Time for $C_{max}$	Observed directly from data as time of first occurrence
$t_{1/2}^a$	Terminal half-life	$\text{Log}_e(2)/k_{el}$ , where $k_{el}$ is the terminal phase rate constant calculated by a linear regression of the log-linear concentration-time curve. Only those data points judged to describe the terminal log-linear decline were used in the regression.

$C_{\text{trough}}$	Predose concentration during multiple dosing	Observed directly from data
CL	Clearance	Dose / $AUC_{\text{inf}}$
$V_z^a$	Apparent volume of distribution	Dose / ( $AUC_{\text{inf}} \cdot k_{\text{el}}$ )
$AUC_{\text{inf}}(\text{dn})^a$	Dose normalized $AUC_{\text{inf}}$	$AUC_{\text{inf}} / \text{Dose}$
$C_{\text{max}}(\text{dn})$	Dose normalized $C_{\text{max}}$	$C_{\text{max}} / \text{Dose}$

a If data permit

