### **5.3.1.1. Pharmacokinetic concentrations**

#### **Concentrations Below the Limit of Quantification**

For all calculations, figures and estimation of individual pharmacokinetic parameters, all concentrations assayed as below the level of quantification (BLQ) will be set to zero. In log-linear plots these values will not be represented. The BLQ values will be excluded from calculations of geometric means and their CIs. A statement similar to ‘All values reported as BLQ have been replaced with zero’ should be included as a footnote to the appropriate tables and figures.

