### **5.3.1.2. Pharmacokinetic parameters**

Actual or nominal PK sampling time will be used for the derivation of PK parameters. If a PK parameter cannot be derived from a patient’s concentration data, the parameter will be coded as NC (ie, not calculated). NC values will not be generated beyond the day that a patient discontinues.

In summary tables, statistics will be calculated by setting NC values to missing. Statistics will not be presented for a particular treatment if more than 50% of the data are NC. For statistical analyses (ie, analysis of variance), PK parameters coded as NC will also be set to missing.

If an individual patient has a known biased estimate of a PK parameter (due for example to a deviation from the assigned dose level), this will be footnoted in summary tables and will not be included in the calculation of summary statistics or statistical analyses.

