##### **6.2.4.1. Avelumab**

$C_{\text{trough}}$  and  $C_{\text{max}}$  for avelumab will be summarized descriptively (n, mean, SD, CV, median, minimum, maximum, geometric mean, its associated CV, and 95% CI) by treatment phase, cycle (if applicable), and day in Arm A. Other standard parameters will be calculated, including but not limited to single and multiple dose  $T_{\text{max}}$ ,  $T_{\text{ss,max}}$ , as data permit.

$C_{\text{trough}}$  and  $C_{\text{max}}$  for avelumab will be plotted for each dose using a box whisker plot by treatment phase, cycle (if applicable), and day within in order to assess the attainment of steady state in Arm A.

Additionally, avelumab PK will be evaluated following cisplatin dosing by comparing the overall geometric mean ratios of  $C_{\text{max}}$  and  $C_{\text{trough}}$  in only Arm A on Day 8 of the CRT Phase to Day 1 of the Lead-in Phase.

Pharmacokinetic parameters for avelumab will be taken from observed values or derived from plasma concentration-time data as described in Section 3.2.4.

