## PK parameters and immunogenicity status

The following analyses will include patients in both the immunogenicity analysis set and in the PK parameter analysis set. The PK endpoints pertinent to the immunogenicity analyses are  $C_{\text{trough}}$  and  $C_{\text{max}}$ .

Blood samples for avelumab PK will be collected pre-dose (within 2 hours before the start of avelumab/placebo infusion) and at the end of infusion (immediately before until 10 minutes after the end of avelumab/placebo infusion) on Days 1 of the Lead-in Phase and Days 8, and 25 of the CRT Phase.

$C_{\text{trough}}$  and  $C_{\text{max}}$  will be summarized descriptively (n, mean, SD, CV, median, minimum, maximum, geometric mean, its associated CV, and 95% CI) by nominal time and ADA status. Linear-linear and log-linear plots of mean and median for  $C_{\text{trough}}$  and  $C_{\text{max}}$  over nominal time and by ADA status will be presented.

Among patients with treatment-induced ADA, analyses will be conducted to assess whether  $C_{\text{trough}}$  and  $C_{\text{max}}$  have any changes before and after the first positive ADA assessment. To be included in this analysis, patients must have the same PK parameter available both before and after the first positive ADA assessment. Relative PK day will be calculated as:

$$(\text{PK assessment nominal day}) - (\text{first positive ADA assessment nominal day}).$$

Nominal day is the protocol scheduled timing for an assessment. For example, if  $C_{\text{trough}}$  is collected on Day 8 of CRT Phase and the first positive ADA result is observed on Day 25 of CRT Phase, then the relative PK day for this  $C_{\text{trough}}$  is -17. Linear-linear and log-linear plots of mean and median for  $C_{\text{trough}}$  and  $C_{\text{max}}$  over relative PK day will be presented.

As data permit, the analyses described above will be repeated for nAb.

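### The planned avelumab Ctrough ratio of CRT Day 8 to Lead-in Day 1 cannot show avelumab PK after cisplatin; Ctrough should be dropped from it and the Cmax ratio kept

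*SAP*

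**What the plan says.** SAP 6.2.4.1, with the same wording in protocol 9.3.2.9.1, evaluates avelumab PK following cisplatin through geometric mean ratios of Cmax and Ctrough, comparing them "in only Arm A on Day 8 of the CRT Phase to Day 1 of the Lead-in Phase". Neither section says which blood sample supplies each Ctrough.

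The surrounding text supplies the rest:

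- **Definition.** SAP Table 3 defines Ctrough as "Predose concentration during multiple dosing", read directly from the data.
- **Labelling.** The worked example in SAP 6.2.7.3 takes a case where Ctrough "is collected on Day 8 of CRT Phase and the first positive ADA result is observed on Day 25 of CRT Phase", and gives it relative day -17. The trough carries the label of the day it was drawn.
- **Sampling.** Protocol Table 2, footnote 19, places pre-dose and end-of-infusion avelumab samples "on Days 1 of the Lead-in Phase and Days 8, and 25 of the CRT Phase". The pre-dose draw is within 2 hours before the infusion. CRT Day 1 has no avelumab sample.
- **Dosing.** The first avelumab dose is on Lead-in Day 1, seven days before CRT Day 1. Later CRT-phase doses are on Days 8, 25 and 39. Cisplatin is on CRT Days 1, 22 and 43.
- **Values below quantification.** SAP 5.3.1.1 sets them to zero for individual parameters, and adds: "The BLQ values will be excluded from calculations of geometric means and their CIs".

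**The concern.** A ratio meant to show avelumab exposure after cisplatin needs a reference from before cisplatin and a comparable sample from after it. For Cmax the named days provide this: the Lead-in Day 1 end-of-infusion sample precedes cisplatin and the CRT Day 8 one follows it. For Ctrough they do not. A pre-dose sample on the day of the first dose is not a trough of anything.

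Two outcomes are possible. Programmed as the SAP labels troughs, the cell is empty. Programmed by preceding dose, it holds a number that reflects the dosing calendar as well as any interaction, and a reader could take it for a cisplatin effect. Avelumab PK is a stated secondary objective with Ctrough as an endpoint, and this is the only comparison in SAP 6.2.4.1 directed at cisplatin's influence on avelumab.

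**Working it through.** **Nominal calendar.** Take Lead-in Day 1 as day 0, so CRT Day d falls on day 6 + d. The SAP's own figure reproduces: 8 - 25 = -17.

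| Visit | Day | Treatment | Avelumab sample |
|---|---|---|---|
| Lead-in Day 1 | 0 | first avelumab | pre-dose, end of infusion |
| CRT Day 1 | 7 | first cisplatin | none |
| CRT Day 8 | 14 | second avelumab | pre-dose, end of infusion |
| CRT Day 22 | 28 | second cisplatin | none |
| CRT Day 25 | 31 | third avelumab | pre-dose, end of infusion |

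**Reading 1: by collection day (the SAP's convention).** The numerator is the day 14 pre-dose sample and the denominator the day 0 pre-dose sample. The denominator precedes any avelumab on study, and protocol 4.2 excludes "Prior immunotherapy with an anti-PD-1, anti-PD-L1, anti-PD-L2, anti-CD137, or anti-CTLA-4 antibody". The value is expected to be below quantification. SAP 5.3.1.1 then removes it from the geometric mean, leaving no valid denominator.

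**Reading 2: by preceding dose.** Protocol 1.2.2.2 describes troughs this way when reporting another trial ("at the end of the first cycle after administration of the 10 mg/kg dose"). The trough of the Lead-in dose is then the CRT Day 8 pre-dose sample, and the trough of the CRT Day 8 dose is the CRT Day 25 pre-dose sample.

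- Time since avelumab: reference 14 - 0 = 14 days; comparison 31 - 14 = 17 days.
- Time since the latest cisplatin dose: reference 14 - 7 = 7 days; comparison 31 - 28 = 3 days.
- Both samples follow the CRT Day 1 cisplatin. The first 7 of the 14 reference days are cisplatin-free, but no trough is taken at their end.
- The Day 25 dose may be given on Days 24 to 29, so with Day 8 on time the later interval runs from 16 to 21 days. The ±2-day CRT visit window adds further variation.
- Protocol 5.5.2.2.1 and 5.5.2.3 allow avelumab on Day 22 when that cisplatin dose cannot be given. If the sample moves with the dose, the intervals become 14 and 14 days, but both samples still follow the CRT Day 1 cisplatin.

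**Value expected with no interaction under reading 2.** Illustrative assumptions: one compartment, equal doses, half-life h in hours, R days to the reference trough and T days to the comparison trough.

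Ratio = 2^(-24(T - R)/h) × (1 + 2^(-24R/h))

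The first factor is the effect of unequal intervals; the second is carry-over from the Lead-in dose. With T = 17 and R = 14, so T - R is 72 h:

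| Half-life (h) | Interval factor | Carry-over factor | Ratio |
|---|---|---|---|
| 74 | 0.509 | 1.043 | 0.53 |
| 102 | 0.613 | 1.102 | 0.68 |
| 130 | 0.681 | 1.167 | 0.80 |

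These half-lives come from the 102 ± 28 h in protocol 1.2.2.2. With equal intervals of 14 days (the Day 22 option), only the carry-over factor remains: 1.04, 1.10 and 1.17.

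**Check against the protocol's own troughs.** The same section reports median troughs of 21, 25 and 27 µg/mL after the first three cycles, then 27 to 36. At 102 h the model gives second/first = 1.10 and steady state/first = 1/(1 - 0.102) = 1.11. The reported figures give 25/21 = 1.19, and 27/21 = 1.29 to 36/21 = 1.71. Solving for the half-life that reproduces each:

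- 1 + 2^(-336/h) = 1.19 gives h of about 140 h, and a 17-versus-14-day ratio of 0.83.
- 1/(1 - 2^(-336/h)) = 1.29 gives about 155 h, and a ratio of 0.89.
- 1/(1 - 2^(-336/h)) = 1.71 gives about 266 h, and a ratio of 1.17.

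Neither the size nor the direction of the displacement from 1 is settled by the documents.

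**The case against.** The strongest reply is that reading 2 has little footing. The SAP's definition and example both point to collection day, and the only preceding-dose wording is a background description of another trial. On the SAP's convention the consequence is an empty cell and no misleading number, the Cmax ratio still addresses the question, and Ctrough by phase, cycle and day is reported anyway. Most of this stands and is why the point is minor. It does not rescue the analysis: the ratio is planned, and it cannot be produced as planned.

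Three stronger inferences are tempting and are not supported:

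- **A trough ratio biased down by about a third.** The 0.68 rests on the terminal half-life in a one-compartment model, which under-predicts the accumulation reported in the protocol. Half-lives matched to that accumulation give 0.83 to 1.17. Those medians rest on changing patient numbers, so they do not settle the matter either.
- **Window extremes as the error of the ratio.** Individual intervals vary with the visit and dosing windows, but the planned statistic is a group geometric mean ratio, and single-patient extremes do not measure its error.
- **Suppression under SAP 5.3.1.2.** That section says "Statistics will not be presented for a particular treatment if more than 50% of the data are NC", but NC is for parameters that cannot be derived. A value below quantification is set to zero, so this rule is not triggered; SAP 5.3.1.1 alone blocks the geometric mean.

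**Conclusion.** The Ctrough ratio of CRT Day 8 to Lead-in Day 1 cannot serve its stated purpose. Under the SAP's convention it has no valid denominator. This assumes that the pre-first-dose sample is below quantification, which is an expectation rather than a certainty; a quantifiable value there would still not be an avelumab trough. Under the preceding-dose reading the ratio can be computed, but it has no pre-cisplatin reference, and with no interaction its expected value is generally not 1. The figures of 0.53 to 0.80 and 0.83 to 1.17 illustrate that dependence and do not estimate a bias.

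A reader might infer that the trial has no valid look at avelumab after cisplatin. The documents do not support that: the Cmax ratio is valid, with samples on either side of the first cisplatin dose. Severity is minor. One descriptive secondary PK comparison is affected; Cmax, PFS and OS are not.

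**What to change.** Delete Ctrough from the CRT Day 8 to Lead-in Day 1 ratio in SAP 6.2.4.1 and keep the Cmax ratio. In the Ctrough summaries already planned by phase, cycle and day, add the actual time since the previous avelumab dose.

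Draw no conclusion about a cisplatin effect on trough from this trial's troughs alone. SAP 6.2.5 and protocol 9.3.2.10 allow population modelling and pooling with other studies, but as an option, and they do not name a cisplatin effect. Any such assessment would have to be specified in the Population Modeling Analysis Plan and would need pooled data without cisplatin, because this trial schedules no pre-cisplatin trough.

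The cost is a wording change with no new samples. Protocol section 9 lets the SAP modify the protocol's plans and requires an amendment only for major changes to the primary endpoint or its analysis, so protocol 9.3.2.9.1 can be aligned at the next amendment.

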#### **9.3.2.9.1. Pharmacokinetic Analysis of Avelumab**

$C_{max}$  and  $C_{trough}$  for avelumab will be summarized descriptively (n, mean, SD, CV, median, minimum, maximum, geometric mean ratios, its associated CV, and 95% CI) by study phase, cycle (if applicable), and day. The trough concentrations for avelumab will be plotted using a box-whisker plot by study phase, cycle (if applicable), and day in order to assess the attainment of steady-state in Arm A.

Additionally, avelumab PK will be evaluated following cisplatin dosing by comparing the overall geometric mean ratios of  $C_{max}$  and  $C_{trough}$  in only Arm A on Day 8 of the CRT Phase to Day 1 of the Lead-in Phase.

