**Figure 1. Study Design Schema**

- a. Patients with LA SCCHN (oral cavity, oropharynx, larynx, or hypopharynx) eligible for front-line treatment: HPV negative disease stage III, IVa, IVb; non-oropharyngeal HPV positive disease stage III, IVa, IVb; HPV positive oropharyngeal disease T4 OR N2c OR N3 (staging per TNM [tumor, node, metastases] guidelines for head and neck sites AJCC 7th Edition). (Note: entry criteria for patients with HPV-positive tumors are different than for HPV-negative tumors).
- b. Avelumab or placebo IV to be administered on Day 1 of the Lead-in Phase (1 week prior to the start of the CRT Phase), and on Days 8, 25, and 39 during the CRT Phase.
- c. SOC CRT = IMRT (70 Gy/35 fractions/7weeks; 1 fraction/day, 5 fractions/week) for 7 weeks + cisplatin (100 mg/m^2 Days 1, 22, 43) during the CRT Phase.
- d. Maintenance Phase to start after completion of the CRT Phase and continue for 12 months.
- e. Patients will continue treatment until confirmed disease progression as assessed by Investigator per modified RECIST v1.1.

AJCC = American Joint Committee on Cancer; CRT = chemoradiotherapy; HPV = human papillomavirus; IMRT = intensity-modulated radiation therapy; LA = locally advanced; Q2W = every 2 weeks; RECIST = Response Evaluation Criteria in Solid Tumors; SCCHN = squamous cell carcinoma of the head and neck; SOC = standard of care.

There will be 3 treatment phases in this study.

- **Lead-in Phase:** On Day 1 of the Lead-in Phase of the study, patients will receive a single dose of avelumab or matching placebo, administered 7 days prior to initiation of the CRT Phase;
- **CRT Phase:** Avelumab or matching placebo will be administered on Days 8, 25, and 39 in conjunction with SOC CRT starting on Day 1 of the CRT Phase;
- **Maintenance Phase:** Following completion of the CRT Phase, avelumab or matching placebo will be administered Q2W for 12 months during the Maintenance Phase.

The treatment schedule is described in Table 2.

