#### CRT Phase

During the CRT Phase, three doses of avelumab are planned to be administered (on Days 8, 25, and 39 of CRT Phase) with a minimum of 14 days required to separate consecutive doses of avelumab or matching-placebo.

**Intended duration of avelumab treatment** in CRT Phase (days) = ((39+14-1)-8+1) = 45

**Duration of exposure to avelumab** in the CRT Phase (days) =

(last dose date of avelumab – first dose date of avelumab + 14)

**Cumulative avelumab dose** (mg/kg) is the sum of the actual doses of avelumab received in the CRT Phase.

**Actual Dose Intensity (DI)** for avelumab in the CRT Phase =

[cumulative dose in the CRT Phase (mg/kg)]/[intended duration of avelumab treatment in CRT Phase (days)/45] (mg/kg/45 days)

**Relative Dose Intensity (RDI)** for avelumab in the CRT Phase is calculated as follows:

- Intended DI (mg/kg/45 days) = 30 (mg/kg/45 days)
- $RDI (\%) = 100 \times [\text{actual DI}] / [\text{intended DI}] = 100 \times \text{actual DI} / 30.$

The summary of treatment exposure and compliance for avelumab in the CRT Phase will include the following information:

- Duration of exposure to avelumab (days);
- Total number of infusions received;
- Cumulative dose (mg/kg);
- Actual DI (mg/kg/45 days);
- RDI (%).

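### With no cisplatin effect, the planned avelumab Cmax ratio is still expected to exceed 1, because it sets a second dose against a first with no carry-over correction

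*SAP*

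**What the plan says.** SAP 6.2.4.1 looks at avelumab after cisplatin by setting one dosing day against another, "in only Arm A on Day 8 of the CRT Phase to Day 1 of the Lead-in Phase". It does this on the geometric mean scale for both Cmax and Ctrough. Protocol 9.3.2.9.1 plans the same comparison: "Additionally, avelumab PK will be evaluated following cisplatin dosing by comparing the overall geometric mean ratios of" those two parameters on the same two days.

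The dosing schedule is in SAP 2.2. The Lead-in dose is "administered 7 days prior to initiation of the CRT Phase", and in the CRT Phase "Avelumab or matching placebo will be administered on Days 8, 25, and 39". Lead-in Day 1 is thus dose one and CRT Day 8 is dose two.

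SAP 3.2.4, Table 3, takes Cmax directly from the data as the highest observed concentration. Neither analysis section gives a pre-dose correction, an accumulation factor or a reference value for the ratio. Samples are taken "pre-dose (within 2 hours before the start of avelumab/placebo infusion) and at the end of infusion" on both days (Protocol Schedule of Activities, Table 2, footnote 19; repeated in SAP 6.2.7.3).

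**The concern.** On Lead-in Day 1 the end-of-infusion concentration comes from one dose given to a patient with no avelumab on board. On CRT Day 8 it is the sum of the second dose and whatever remains of the first. The ratio of the two exceeds 1 whenever drug is left over, whether or not cisplatin was given in between.

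The ratio is introduced as an evaluation of avelumab after cisplatin, and no other explanation for a departure from 1 is offered. A reader who takes 1 as the no-effect value could see an increase where there is none, or miss a decrease of similar size. No concurrent control can absorb the problem, because Arm B receives no avelumab. The reverse question, avelumab's effect on cisplatin (SAP 6.2.4.2), is compared between arms on the same day and is free of it.

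The point is confined to Cmax. The Ctrough ratio in the same sentence raises separate questions of definition.

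**Working it through.** The documents state no expected ratio or accumulation factor, so there is no figure of theirs to reproduce.

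**Inputs**
- Interval between doses: 7 days (Lead-in Day 1 to CRT Day 1) + 7 days (CRT Day 1 to Day 8) = 14 days = 336 h. SAP 6.5.3.1 describes the CRT Phase dosing "with a minimum of 14 days required to separate consecutive doses of avelumab or matching-placebo". Table 2 of the protocol's Schedule of Activities allows ±2 days per CRT visit, that is 288 to 384 h.
- Half-life: for the "terminal half-life of 10 mg/kg" dose, Protocol 1.2.2.2 gives 102 ± 28 h. One SD either side is 74 to 130 h.
- Median troughs at 10 mg/kg (same section): 21, 25 and 27 µg/mL after cycles one, two and three.

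**No-effect ratio.** With linear superposition and mono-exponential decline, Cmax(dose 2)/Cmax(dose 1) = 1 + 2^(−interval/half-life).

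| Interval (h) | Half-life (h) | Residual fraction | No-effect ratio |
|---|---|---|---|
| 336 | 102 | 0.102 | 1.10 |
| 336 | 74 | 0.043 | 1.04 |
| 336 | 130 | 0.167 | 1.17 |
| 288 | 102 | 0.141 | 1.14 |
| 384 | 102 | 0.074 | 1.07 |

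Letting half-life vary log-normally between patients with CV 28/102 leaves the geometric mean ratio at 1.102.

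**Check against the troughs.** The observed trough ratio is 25/21 = 1.19, against 1.10 from the formula, which would imply a half-life of about 140 h. These are medians from different numbers of patients (283 and 269), so the check is loose, but it confirms carry-over. The documents give no first-dose Cmax. If it lay between 125 and 500 µg/mL (an assumption), a 21 µg/mL residue would add 21/125 = 17% down to 21/500 = 4%.

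**What could be hidden.** With the residue unchanged, an observed ratio of 1.00 needs the second dose's own contribution to be 1 − 0.102 = 0.898 of the first. A fall of about 10% would then look like no effect.

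**Precision.** Avelumab is sampled in all patients, and Arm A has about 640/2 = 320. The documents give no variance. Assuming 300 paired patients and an SD of the log ratio of 0.3 to 0.5, the 95% half-width is 1.96 × 0.3/√300 = 0.034 to 1.96 × 0.5/√300 = 0.057. A shift of 10% could then be estimated quite precisely.

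**Subtracted ratio.** Take (Day 8 end-of-infusion − Day 8 pre-dose)/(Lead-in Day 1 end-of-infusion). The residue falls only to 2^(−1/102) = 0.993 of itself during the one-hour infusion, so the no-effect value is about 1.00.

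**Its blind spot.** Suppose, for illustration, that clearance rose by 20% from CRT Day 1, the midpoint of the interval. The half-life over the last 168 h becomes 102/1.2 = 85 h, and the residue is 2^(−168/102) × 2^(−168/85) = 0.319 × 0.254 = 0.081 instead of 0.102. The Day 8 pre-dose concentration drops by about 20%, the planned ratio moves from 1.10 to 1.08, and the subtracted ratio stays at about 1.00.

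**The case against.** The strongest reply is that the plan never claims more than description. It sets no hypothesis, equivalence limits, reference value or decision rule. A reader might infer that the plan attributes the whole Day 8 difference to cisplatin, but the documents do not say so. SAP 6.2.4.1 also summarises and plots Cmax and Ctrough by day to judge approach to steady state, so the Day 8 pre-dose level will be in view. Population modelling, which accounts for dose history, is allowed for in SAP 6.2.5 and Protocol 9.3.2.10. This stands as a limit on the point. It does not remove it: the daily summaries leave the ratio uncorrected, and the modelling is optional and may be reported separately.

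Second, a reader might take 10% as established. It is not. It applies a terminal half-life to the whole end-of-infusion peak, and any distribution phase would make the residue a smaller share of that peak. The actual interval also varies with visit windows and IMRT delays. The size is therefore uncertain; the upward direction is not.

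Third, subtraction discards information. Cisplatin falls midway between the two doses, so an effect on clearance would show mainly in the Day 8 pre-dose concentration, the quantity being subtracted. This objection stands, and it rules out using the subtracted ratio as a replacement.

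Finally, little depends on the result. Protocol 1.2.2.2 places at least 95% receptor occupancy at 1 µg/mL, against a first-cycle median trough of 21 µg/mL.

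**Conclusion.** The point holds as a matter of interpretation. The only pre-specified comparison for a cisplatin effect on avelumab Cmax sets dose two against dose one without correcting for carry-over. Its no-effect value is above 1: roughly 1.10, and about 1.04 to 1.17 across half-lives of 74 to 130 h. This rests on mono-exponential decline, linear superposition and a 336 h interval. The range reflects the spread in half-life only, not error in the model.

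It would be wrong to read this as a flaw in the trial's efficacy or dosing conclusions. The comparison is descriptive and secondary, and no decision in the documents turns on it. Nor does removing carry-over isolate cisplatin, because IMRT and elapsed time also separate the two days.

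**What to change.** In SAP 6.2.4.1:

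1. Keep the planned Cmax ratio, and add a sentence saying that CRT Day 8 is the second dose, so accumulation puts the ratio's no-effect value above 1. Give the expected value with its range and assumptions.
2. Report beside it the geometric mean ratio of (Day 8 end-of-infusion minus Day 8 pre-dose) to the Lead-in Day 1 end-of-infusion concentration.
3. State that the subtracted ratio is largely insensitive to a change in clearance, which should be looked for in the Day 8 pre-dose concentration.

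The cost is a few lines of SAP text and one derived variable. No new samples are needed. The subtracted value carries slightly more assay noise, and patients without a usable Day 8 pre-dose result drop out of that ratio. Protocol 9.3.2.9.1 can stand, since the planned comparison is retained.
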